Title: Botulinum toxin is a promising prophylactic therapy for minimizing post-excisional scarring: A Double Blinded, Randomized Controlled Trial

PI: [name]

PI: [name]

NCT02623829

Document Date: 7/9/2015

Botulinum toxin is a promising prophylactic therapy for minimizing post-excisional scarring:

A Double Blinded, Randomized Controlled Trial

Investigators:

[name]

[name]

Study Site:

Mount Sinai School of Medicine

Department of Dermatology

[name]

[name]

Financial Support:

Protocol Version: 1, 7/9/2015

Botulinum toxin is a promising prophylactic therapy for minimizing post-excisional scarring: A Double Blinded, Randomized Controlled Trial

Introduction and Rationale:

Dermatological surgeons wear many hats to care for subjects with skin cancer. While their role in cancerous tissue removal results in superior cure rates, there is also a need for skilled excisional repair and effective wound healing regimens so the subject can heal with the least amount of scarring necessary. As such, numerous techniques have been developed for reducing the morbidity associated with excessive scarring. Various flaps and grafts allow the surgeon to approximate skin texture, thickness and adnexa with respect to the residual surrounding tissue. However, for optimal cosmetic and functional outcome, specific suture techniques are often necessary to ensure close wound approximation while simultaneously minimizing static tension along the wound edge (1). In addition, there are post-operative techniques for wound care that range from special dressings during the various stages of healing to cosmetic procedures for scar modification. Unfortunately, once the operation is complete, there is little the surgeon can do to minimize adverse scar formation without impairing the healing process. To date, most surgical wounds are allowed to heal at least partially before scar revision or modulation is attempted.

Botulinum toxin presents a unique opportunity for surgeons to affect scar formation throughout the duration of the healing process. These effects are likely independent and adjunctive to any and all wound care techniques, and are primarily attributed to a reduction in dynamic tension on the wound edges (1). Most importantly, botulinum toxin's one time dosing requirements with respect to reduced scar formation precludes the variance inherent to standard wound care practices.

Therefore, it has been proposed that for selected subjects, botulinum toxin may be a safe, effective and reliable means for improved post-excisional repair outcomes (2). Botulinum toxin has been investigated as an inhibitor of excessive, post-excisional scar formation in plastic surgery and Otorhinolaryngology literature (1-7). However, these promising studies have yet to combine objective assessment measures of human scar formation in a randomized controlled trial. In addition, there are currently no formal studies of botulinum toxin as a prophylactic against excess scarring in the dermatological literature. Fortunately, Botulinum toxin dosing in the forehead for the purposes of inhibiting excessive scar formation is comparable to the amount given for cosmetic purposes (5), which is commonplace in dermatology and well-studied (6-8).

Objective:

This study will attempt to assess the efficacy of Botulinum toxin as a prophylactic treatment in post-excisional repairs for the purpose of preventing excess scar formation. The end points will be the evaluation of each scar using the Manchester Scar Scale.

Description of Study:

We plan to enroll 40 subjects in this study who are scheduled for forehead excisions on the day of enrollment. Each qualifying subject will undergo post-excisional injections into the forehead and glabella. Twenty will receive 1ml of normal saline and 20 will receive a total of 50 units of botulinum toxin diluted in 1ml of normal saline. Both the subject and investigator will be blinded as to which site receives what. After these injections, the subject will proceed as per the normal standard of care for their post-operative care. Upon return for suture removal about a week later (as per normal standard of care), the subjects will all answer a brief questionnaire regarding any adverse events they may have had after the injections. They will then be scheduled for their last and only additional clinical visit for this study, at 24 weeks. Upon arrival for the final visit, the patient will again answer a brief questionnaire regarding any adverse events they may have had after the injections. After this, the assessment of response will be made utilizing the Manchester Scar Scale (MSS) both clinically and in a modified version via standardized photographs taken of the scar. The patient will then be discharged home, with their involvement in the study complete.

Method of injection:

Either 1ml of normal saline or 50 units of botulinum toxin diluted in 1ml of normal saline will be administered to a randomly assigned subject. The procedure will be identical for either substance. The forehead will be injected with 12, evenly spaced and symmetrical aliquots of 0.05ml and the glabella will be injected at the nasal root and the medial aspect of the corrugators with 0.1ml each in addition to the lateral aspect of each corrugator with 0.05ml. The injections will be administered with a 30G needle perpendicular to the skin. The following diagram (labeled figure 1) depicts the injection pattern:

Figure 1

*Large red circles represent areas for injecting 5units of Botox or 0.1ml of normal saline

*Small blue circles represent areas for injecting 2.5units of Botox or 0.05ml of normal saline

Response Measures:

The Manchester Scar Scale, a validated scale able to be used for linear surgical scars, will be applied in 2 ways (9-11). These 2 scores will then be added to yield the overall scar assessment score for each scar at each visit. Individual scores will be determined as follows:

1) Manchester Scar Scale (MSS)

The MSS will be used to clinically assess the scar of each subject at each visit with the following criteria clinical assessment sheet:

Clinical Assessment Sheet			
		Visual Analogue Scale	Poor
Excellent			
Lighter or Darker	A	Color (cf. to surrounding skin)	Poor
		Perfect	1
		Slight mismatch	2
		Obvious mismatch	3
		Gross mismatch	4
	B	Matte (1)/shiny (2)	
		Contour	
		Flush with surrounding skin	1
		Slightly proud/indented	2
	C	Hypertrophic	3
		Keloid	4
		Distortion	
		None	1
		Mild	2
	D	Moderate	3
		Severe	4
		Texture	
		Normal	1
	E	Just palpable	2
		Firm	3
		Hard	4

The Visual Analog Scale is on a 10cm line with a zero signifying the worst possible outcome and 100 representing the complete absence of noticeable scarring. This is a global, subjective assessment that is combined with a more objective assessment based on scar color, reflectance of light, contour, distortion and texture. A summation of the VAS score (rounded to the nearest cm) and the values assigned for each of the aforementioned assessment criteria will then be determined.

2) Modified Manchester Scar Scale (mMSS)

The mMSS will employ much of the MSS but will not include the assessment for texture since it will be applied to standardized photographs of each scar from each visit. Photographs will be taken at a distance of 10cm and cropped to include the scar and surrounding 1cm of normal skin. These photographs will then be assessed by a panel of Dermatologists at a later date. The scores will then be averaged to yield the mMSS average score for each scar at each visit.

Subject Selection:

Inclusion Criteria

1. English-speaking adults at least 18 years old.
2. Subjects must be scheduled for an excision of forehead skin due to any etiology, with a simple linear closure planned as the most likely surgical repair.
3. Subjects must be able to read, sign, and understand the informed consent.
4. Subject is willing and able to participate in the study as an outpatient, making several visits to the study center during the treatment and follow-up periods and to comply with all study requirements including concomitant medication and other treatment restrictions.
5. If subject is a female of childbearing potential she must have a negative urine pregnancy test result prior to study treatment initiation and must agree to use an approved method of birth control while enrolled in the study.

Exclusion Criteria

1. Subjects with an unstable medical condition as deemed by the clinical investigator, including review of the subject's prior and current medications.
2. Subjects with Myasthenia gravis, Lambert-Eaton Syndrome or other neuromuscular disorder.
3. Subjects taking medications that may alter the function of neuromuscular junctions (i.e. aminoglycoside antibiotics)
4. Women who are pregnant, lactating, or planning to become pregnant during the study period.
5. Subjects who have a history of keloids.
6. Known allergy to botulinum toxin.
7. Subjects who are not able to be closed with a simple linear technique

Informed Consent:

Prior to entering the study, the investigator or designated assistant will explain to each subject the nature of the study, its purpose, procedures, expected duration, alternative therapy available, and the benefits and risks involved in study participation. Subjects will be given the consent document, the opportunity to ask questions, and will be informed of their right to withdraw from the study at any time without prejudice. After this explanation and before any study-specific procedures have been performed, the subject will voluntarily sign and date and informed consent form, including photographic consent. Prior to participation in the study, the subject will receive a copy of the signed and dated written informed consent form.

Study Methodologies:

Visit 1 Screening/Baseline – Day 0 / Receive Injection

The following pre-study screening procedures should be completed prior to randomization and Treatment Initiation:

1. Obtain a signed and dated subject informed consent, including photographic authorization.
2. Review inclusion and exclusion criteria.
3. Collect demographic information including date of birth, sex, race, ethnicity, and underlying reason for excision.
4. If applicable, perform urine pregnancy testing.
5. After the excision is completed, the length of the defect will be recorded in addition to the number and type of sutures placed, final length of suture line and a photograph will be taken.
6. The subject will be randomly assigned to receive normal saline with or without botulinum toxin, prepared by outside party (recorded separately) and handed to dispensing physician and neither injector nor subject will know which.
7. Contents of syringe will be administered to forehead and glabella.
8. Schedule week 2 visit.

Visit 2 (Week 1 +/- 2 days, at suture removal as per normal standard of care)

The following procedures will be performed at this visit:

1. Review and record adverse events.
2. Sutures will be removed and unidentifiable photographs will be taken of the forehead.
3. Schedule final visit.

Visit 3 (Week 24 +/- 2 days)

The following procedures will be performed at this visit:

1. Review and record adverse events.
2. Subject will have their scar assessed clinically via the MSS and be photographed for later mMSS assessments.

Note: any treatment-related AEs or LSRs that are ongoing will be followed to resolution or to the investigator's satisfaction.

Primary Endpoints

- 1) Difference between treated and control MSS scores for each scar at 6 months
- 2) Difference between treated and control average mMSS scores for each scar at 6 months
- 3) Difference between treated and control aggregate scores for each scar at 6 months

Lesion Assessment Guidelines:

All MSS and mMSS assessments will be performed in a standardized fashion. The mMSS assessments will be blinded and performed by board-certified dermatologists in the Department of Dermatology, Faculty Practice Associates, Icahn School of Medicine at Mount Sinai, New York City.

Botulinum and Saline Injection Guidelines:

50 units of Botulinum toxin will be injected into randomly assigned subjects. The same procedure will be carried out for administration of the saline.

Safety Evaluations:

Urine Pregnancy Tests

Females of childbearing potential will undergo a urine pregnancy test at Visit 1(Week 0). If the pregnancy test is positive at Visit 1 the subject will not be permitted to enroll in the study and will not receive study drug.

Adverse Reactions

At each visit, the subjects will be assessed for any of the following possible AEs:

- injection site pain
- ecchymosis
- eyelid/brow ptosis
- systemic effects, including nausea, fatigue, malaise, flu-like symptoms, headache, runny nose, diplopia, dysarthria, generalized muscle weakness, asthenia, blurry vision, ptosis, dysphagia, dystonia, urinary incontinence, breathing difficulties, rash.

Prior and Concomitant Medications:

At the initial visit, prior and concomitant medications and therapies will be reviewed as may pertain to exclusion from the study.

Restricted Medications/Treatments

Restricted medications and treatments prior to the study initiation are those that the investigator feels may indicate that the subject has an unstable medical condition, as described in the exclusionary criteria.

Subject Withdrawal or Discontinuation:

Subjects may choose to withdraw from the study or may be withdrawn by the investigator at any time without prejudice to their future medical care. Any subject who does not comply with the inclusion/exclusion criteria may be withdrawn from further participation in the study.

Discontinuation Procedures: Any subject who wishes to discontinue prematurely from the study should return to the study center for an End of Study Visit.

Adverse Event Definitions:

An adverse event (AE) is any untoward medical occurrence in a subject or clinical investigation subject which is temporally related to protocol procedures, including administration of a pharmaceutical product at any dose, but which does not necessarily have a causal relationship with the treatment. The term AE also applies to laboratory findings or results of other diagnostic procedures that are considered to be clinically relevant (e.g., that required unscheduled diagnostic procedures or treatment measures or result in withdrawal from the study). Surgical procedures themselves are not adverse events; they are therapeutic measures for conditions that require surgery. The condition for which the surgery is required is an adverse event, if it occurs or is detected during the study period. Planned surgical measures permitted by the clinical study protocol and the condition(s) leading to these measures are not adverse events, if the condition(s) was (were) known before the start of study treatment.

Adverse events will be recorded according to CTCAE guidelines.

A serious adverse event (SAE) is any AE or adverse drug reaction that at any dose results in any of the following outcomes:

- death
- life-threatening adverse event
- inpatient hospitalization or prolongation of existing hospitalization
- persistent or significant disability/incapacity
- congenital anomaly/birth defect

An event may be considered serious when, based upon appropriate medical judgment, it jeopardizes the subject and may require medical or surgical intervention to prevent one of the outcomes listed above.

A life-threatening adverse event is any AE or adverse drug reaction that at any dose places the subject, in the view of the investigator, at immediate risk of death from the reaction as it occurred. It does not include a reaction or event that, had it occurred in a more severe form, might have caused death.

Materials and Supplies:

Study Drug

Botox botulinum toxin will be used for this study, a grant from Allergan to provide drug is pending. Normal saline will be used as the placebo.

1cc Syringes and 30 G needles will be used.

Gauze and alcohol swabs will be used to prepare the injection sites.

Institutional Review Board:

Prior to beginning this study, approval must be obtained from the Institutional Review Board at the Icahn School of Medicine at Mount Sinai.

Data Analysis:

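### At Visit 3 the adverse-event questionnaire precedes the clinical MSS, and nothing keeps its answers from the unnamed MSS rater (minor; free to fix)

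*Combined protocol and SAP*

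**What the plan says.** **Order at the final visit.** The Description of Study puts the questionnaire first: "Upon arrival for the final visit, the patient will again answer a brief questionnaire regarding any adverse events". The scar rating follows: "After this, the assessment of response will be made utilizing the Manchester Scar Scale (MSS) both clinically". Under Study Methodologies, the Visit 3 list has the same order. Adverse-event review is item 1, and item 2 reads "Subject will have their scar assessed clinically via the MSS and be photographed for later mMSS assessments".

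**Earlier adverse-event review.** At the suture-removal visit, "the subjects will all answer a brief questionnaire regarding any adverse events they may have had after the injections". Study Methodologies places this at "Visit 2 (Week 1 +/- 2 days, at suture removal as per normal standard of care".

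**What is asked.** The questionnaire itself is not printed. Safety Evaluations, Adverse Reactions, says "At each visit, the subjects will be assessed for any of the following possible AEs", and the list that follows includes ptosis of the eyelid or brow.

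**Blinding.** The Description of Study states: "Both the subject and investigator will be blinded as to which site receives what". The Visit 1 list says of the syringe that "neither injector nor subject will know which". The Lesion Assessment Guidelines say that the mMSS ratings are blinded and done by board-certified dermatologists. Of the clinical MSS they say only that it is standardized, and they name no rater.

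**Role of the MSS.** It is primary endpoint 1 and one component of the aggregate score, endpoint 3. Response Measures describes its visual analogue component as global and subjective.

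**The concern.** Blinding of the syringe does not stop a rater from guessing the arm from what a subject reports. The control is saline. The Introduction attributes the drug's benefit to lower dynamic tension at the wound, and the exclusion criteria bar medicines that may alter neuromuscular junction function. Against that background, a subject who reports a drooping brow may be taken for an active-arm subject. If the rater hears this minutes before scoring, the visual analogue score and the graded items could follow expectation rather than the scar.

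Because the questionnaire covers events since the injections, an event that has resolved by week 24 can still be raised immediately before scoring. The Visit 2 review is a second route if the same person later scores the MSS. What is at stake is the credibility of one primary endpoint and, through it, of the aggregate.

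**Working it through.** **Step 1: does the text close the gap?** The plan has no figure of its own on this point, so the sections are set side by side.

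| Question | Clinical MSS | mMSS |
|---|---|---|
| Rater identified? | No (Visit 3 list and Lesion Assessment Guidelines) | Yes, a panel of board-certified dermatologists |
| Blinding stated for the assessment? | Not specifically; only the general statement about subject and investigator | Yes |
| Timing relative to adverse-event answers | Directly after them, same visit | Later, from cropped photographs |
| Rater kept from adverse-event answers? | Not stated | Not stated, but the rating is made from photographs |

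The order is explicit in the Description of Study. The Visit 3 list agrees with it but does not itself say that its items are sequential.

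**Step 2: how large could the effect be?** The documents give 20 subjects per arm and the Wilcoxon rank sum test (Data Analysis). They give no significance level, SD or event rate, so these are assumed:
- two-sided 5% level, no true treatment effect, normally distributed scores;
- MSS SD of 2, 3 or 4 points;
- a share f of active subjects, and no saline subjects, gives a cue;
- each cued subject's MSS total moves by one net point, always in the same direction.

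The average between-arm shift in SD units is f × 1 / SD. For example, f = 0.20 and SD = 2 give 0.20 × 1 / 2 = 0.10 SD; f = 0.50 and SD = 2 give 0.50 × 1 / 2 = 0.25 SD.

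False-positive rates from 100,000 simulated trials per case, normal approximation with continuity correction:

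| MSS SD | f = 20%: average shift | f = 20%: rate | f = 50%: average shift | f = 50%: rate |
|---|---|---|---|---|
| 2 | 0.10 SD | 5.8% | 0.25 SD | 11.3% |
| 3 | 0.07 SD | 5.4% | 0.17 SD | 7.8% |
| 4 | 0.05 SD | 5.2% | 0.125 SD | 6.5% |

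With no shift the simulated rate is 4.8%, so the first of the two rate columns is close to nominal.

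**Step 3: which test do these rates describe?** They apply to the MSS tested on its own. Primary Endpoints lists it separately, but Data Analysis can be read as testing only the sum of MSS and mMSS. Adding a score that is not shifted dilutes the effect. With an average MSS shift of 0.10 SD spread over the whole active arm, mMSS SD 0.5 to 1.25 times the MSS SD, and correlation 0.5 or 0.7, the rate for the sum is 5.1 to 5.4%.

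**The case against.** **The trial is already double-blind.** This stands as far as it goes. Subject and investigator are blinded, and an outside party prepares the syringe. If the MSS rater is an investigator, the general statement covers that person. A reader might infer that the MSS is scored open-label because blinding is repeated only for the mMSS. The documents do not support that. What is missing is protection against guessing the arm.

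**Each link in the chain is inferred.** This is also correct. The protocol does not say that the rater gives or reads the questionnaire. It does not say that ptosis distinguishes the arms, and it gives no rates. The argument from saline control and neuromuscular action is reasonable, but it is not a statement in the plan.

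**The effect could be made to look large.** A reader might assume a half-SD shift in the MSS and conclude that the error rate reaches about 32%. That figure requires every active subject to shift by half an SD. Here only cued subjects would shift. With 20% cued and an SD of 2 to 4, an average of 0.50 SD would need 0.50 × 2 / 0.20 = 5 to 0.50 × 4 / 0.20 = 10 net points per cued subject. Nothing in the documents suggests that.

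**The mMSS.** A reader might extend the concern to the mMSS because its panel is in the same department. The plan states that those ratings are blinded, and they are made later from cropped photographs. Shared affiliation is not evidence of exposure.

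**Conclusion.** The point holds as a minor design weakness. The stated order puts possibly arm-suggestive information immediately before the clinical MSS, and no provision keeps it from the rater. Functional unblinding is possible, not shown.

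On the assumptions above, the false-positive rate for the MSS stays at about 5 to 6% with 20% of active subjects cued. It reaches about 6.5 to 11% only if half are cued and every cued score moves the same way. The documents fix neither the share cued nor the size or direction of any shift, so these are illustrations and not estimates of bias in this trial. The point is worth acting on because the correction is free, not because the expected bias is large.

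**What to change.** 1. In the Description of Study and in the Visit 3 list under Study Methodologies, have the clinical MSS scored and recorded and the photographs taken first. Give the adverse-event questionnaire afterwards.
2. In the Lesion Assessment Guidelines, add that the clinical MSS rater is blinded to allocation and does not consult adverse-event records before the score is recorded.

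Cost: none beyond the wording. The visit and the data collected are unchanged, and the change needs no extra staff.

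What remains: reordering Visit 3 does not remove what a rater may have learned at the Visit 2 adverse-event review. If existing staffing allows a different person to score the MSS, that route closes too, at the price of a small scheduling constraint. Cues visible on the forehead at week 24 could also remain.

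### Rounding the VAS to whole centimetres before summing costs a little precision in the MSS and the aggregate; recording it to 0.1 cm would cost almost nothing

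*Combined protocol and SAP*

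**What the plan says.** The scoring rule is in the Response Measures section, item 1 (MSS). The VAS is described as follows: "The Visual Analog Scale is on a 10cm line with a zero signifying the worst possible outcome and 100 representing the complete absence" of visible scarring. The next step is "A summation of the VAS score (rounded to the nearest cm", combined with "the values assigned for each of the aforementioned assessment criteria will then be determined". The items are colour (1 to 4), matte or shiny (1 to 2), contour, distortion and texture (1 to 4 each), and 1 is the best value on each graded item. No reason is given for the rounding.

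Item 2 of the same section defines the photographic version: "The mMSS will employ much of the MSS but will not include the assessment for texture". Each scar is scored by a panel of unstated size, and "The scores will then be averaged to yield the mMSS average score for each scar at each visit". Rounding is not mentioned there.

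The aggregate is the MSS plus the mMSS: "These 2 scores will then be added to yield the overall scar assessment score for each scar at each visit". All three scores are listed under Primary Endpoints at 6 months. Data Analysis plans a Wilcoxon rank sum test and does not mention ties. Description of Study gives 20 subjects per arm, without a power calculation.

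**The concern.** Every component of the MSS other than the VAS has two or four levels. The VAS is the only part that can separate scars finely, and the scoring rule reduces it to whole numbers before it is used. Rounding adds measurement error unrelated to treatment and turns the total into an integer, so many subjects share a value. A rank-based test on 20 per arm then has less ordering information to work with. At stake is a little power, given up without any stated benefit.

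**Working it through.** The plan gives no SD, effect size, alpha or power, so there is no planned figure to reproduce. The values marked as assumed below are mine.

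**Resolution of the MSS.** The item sum runs from 1+1+1+1+1 = 5 to 4+2+4+4+4 = 18. Adding a VAS of 0 to 10 gives a total from 5 to 28. In whole numbers that is 28 − 5 + 1 = 24 possible values. In steps of 0.1 it is (28 − 5)/0.1 + 1 = 231.

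**Variance added.** Rounding to a 1 cm grid adds an approximately uniform error with variance 1/12 = 0.0833 cm². Assume VAS SD 1.5 cm, item-sum SD 2 and correlation ρ. The variance of the total is 1.5² + 2² + 2ρ(1.5)(2) = 6.25 + 6ρ.
- Directions aligned, ρ = +0.6: 6.25 + 3.6 = 9.85, and 0.0833/9.85 = 0.00846, about 0.8%.
- Summed as written (high VAS good, high items bad), ρ = −0.6: 6.25 − 3.6 = 2.65, and 0.0833/2.65 = 0.0314, about 3%.

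**Analytic power on a total score.** 20 per arm, two-sided alpha 0.05, assumed effect 0.9 SD, two-sample comparison of means. Power without rounding is 81.2% throughout.

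| Total-score SD | Rounding share of variance | Power with rounding | N per arm for 80%: unrounded / rounded |
|---|---|---|---|
| 1 | 8.3% | 78.1% | 20 / 21 |
| 1.5 | 3.7% | 79.8% | 20 / 21 |
| 2 | 2.1% | 80.4% | 20 / 20 |
| 3 | 0.9% | 80.9% | 20 / 20 |
| 4 | 0.5% | 81.0% | 20 / 20 |

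**Simulated rank-sum power on the MSS.** 6,000 trials per setting, 20 per arm, tie-corrected test, shift of 0.9 SD in a latent severity that drives both the VAS and the items. The same simulated data are scored both ways.

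| VAS SD (cm) | Aligned, mm | Aligned, whole cm | As written, mm | As written, whole cm |
|---|---|---|---|---|
| 1 | 68.8% | 68.3% | 42.5% | 42.0% |
| 1.5 | 69.2% | 68.8% | 22.6% | 22.2% |
| 2 | 68.8% | 68.5% | 11.2% | 11.0% |
| 2.5 | 68.1% | 67.3% | 6.0% | 6.1% |

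The loss from rounding is 0.3 to 0.8 points when aligned, and between −0.1 and 0.5 as written. A larger run (20,000 trials per setting) gave 0.2 to 0.3 points aligned and 0.2 to 0.8 as written. In that run 2% to 5% of individual trials crossed p = 0.05, in one direction or the other, because of rounding alone.

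**Ties and validity (6,000-trial run).** With directions aligned, about 88% to 92% of subjects share an MSS value when the VAS is rounded, against 25% to 32% in millimetres. As written, the figures are 96% against 44% to 49%. Type I error is 4.6% to 5.0% under either rule.

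**mMSS, if the same rule applies.** With an assumed three raters whose rounding errors are independent, averaging reduces the added variance to 1/(12 × 3) = 0.028 cm². Simulated power with directions aligned is 73.3% in mm and 73.4% rounded at VAS SD 1.5 cm, and 73.9% and 74.0% at SD 2 cm: no loss. Shared values still fall from 65–68% to 11%.

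**The case against.** The strongest reply is that this is a preference about precision with almost no effect on the endpoints. Ties do not invalidate a tie-corrected rank-sum test, and integer items remain in every total whatever is done to the VAS. In a smaller simulation (3,000 trials per setting, three raters), the differences on all three endpoints were within 0.4 points when directions were aligned, and ranged from nil to 1.8 points as written. The directional conflict between the VAS and the items matters far more. In the table above, the as-written columns lie about 26 to 62 points below the aligned ones. Removing the rounding alone would yield a finer version of a sum whose parts offset each other.

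All of this stands, and it sets the size of the point. It does not show that the rounding does any good.

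A reader might infer three stronger things that the documents do not support:
- **That rounding affects every primary score.** It is written only for the MSS and enters the aggregate through it. For the mMSS it is an inference from a general statement that most of the MSS is reused.
- **That up to about 3 points of power are lost.** A loss of that size appears for the VAS analysed alone at an SD of 1 cm, or for a total score with an SD near 1. The VAS alone is not an endpoint, and no document supports so small a total-score SD.
- **That a millimetre reading has already been recorded.** The assessment sheet shows a line to be marked, with no numeric field.

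**Conclusion.** The point holds as a minor, low-cost improvement in precision. Whole-centimetre rounding discards available detail and sharply increases ties in the MSS. It also enters the aggregate, and the mMSS if the rule is meant to carry over. Simulated power on the MSS falls by under about 1 point, there is little or no loss on a three-rater mMSS with directions aligned, and validity is not threatened. These sizes rest on assumed SDs, correlations, effect size, alpha and panel size, and on a tie-corrected test, which Data Analysis does not specify. The conflict of direction in the same paragraph is the larger fault, and the rounding should be treated as secondary to it.

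**What to change.** In Response Measures, item 1, delete the parenthesis that rounds the VAS. State that the mark is measured to the nearest millimetre, entered in centimetres with one decimal (0.0 to 10.0), and summed in that form. The unit must be explicit, because adding a raw 0-to-100 reading would let the VAS dominate the items. In item 2, state that the same rule applies to each panel rater's VAS before averaging.

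In the same edit, align the directions before summing, for example by using 10 minus the VAS reading so that higher is worse throughout. It would also help to name the tie-corrected form of the test in Data Analysis, since some ties will remain.

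The cost is a phrase in each scoring paragraph and a one-decimal entry field. No extra data, staff or visits are needed.
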